We hypothesize that disruption of the sleep-wake cycle by sleep restriction increases risk for CKD, potentially via an increase in aldosterone secretion and reduction of nocturnal melatonin secretion with its pleiotropic effects on blood pressure, glucose metabolism, and endothelial function. We also hypothesize that correction of circadian disruption in high-risk, habitually sleep-restricted individuals by sleep extension or by melatonin supplementation using a controlled-release formulation administered at bedtime can reduce overall risk for CKD. These hypotheses give rise to the following specific aim:

1. Sleep extension and melatonin supplementation and CKD risk factors

In a 6 week pilot study, 20 individuals with habitual sleep restriction will all be asked to extend their nightly sleep by 1 hour, and will then be randomized 1:1 to nightly controlled-release oral melatonin (2mg) or placebo. We will assess whether sleep extension and nightly melatonin supplementation in the community is a feasible intervention with a beneficial effect on the following CKD risk factors: systemic and renal specific RAAS activation (systemic plasma renin activity, plasma angiotensin II

levels, 24-hour urine aldosterone excretion, and renal plasma flow response to captopril); nocturnal blood pressure measured by 24-hour ambulatory blood pressure monitor; central blood pressure measured by pulse wave analysis; and glucose metabolism measured by Minimal Model assessment of insulin resistance and β -cell response to a mixed meal protocol.

Subject Selection

An obese, pre-diabetic, pre-hypertensive population with habitual sleep restriction is ideally suited for a study of the effects of sleep extension and melatonin on CKD risk factors. We have shown that obesity and insulin resistance are associated with reduced endogenous melatonin secretion.^{39,64} Obesity predisposes individuals to aldosterone mediated inflammation and endothelial dysfunction. Thus, measures that reduce aldosterone secretion in these individuals may be particularly beneficial.^{10,23,65}

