We will recruit individuals from the Boston area who meet the inclusion and exclusion criteria listed in **Table 5**. Recruitment will take place through several venues. First, we will recruit from those who have already completed our MODERATE randomized trial (N>200 who have completed so far). The vast majority these individuals still reside in Boston. MODERATE participants have provided consent to be re-contacted for future studies. We will use the MODERATE database to identify individuals who may be eligible for our study, and contact them directly to invite them to participate.

Second, we will simultaneously attempt to enroll study participants who fulfill the age and BMI requirements using routine media outlets in the local community and also online advertising. These include: (1) billboards placed in Boston mass-transit buses and subways; (2) advertisements in local print media, such as the Boston Metro and the Boston Globe; (3) online advertisement with websites such as Craig's List and Oodle (these sites have been productive sources for recruitment in the past).

Third, we will use recruitment opportunities provided through Partners, such as Partners RSVP, and ClinicalTrials@Partners.

We will include both men and women and all races and ethnicities. The only exception will be women who are pregnant because certain medications used during the inpatient evaluations (e.g., nitroglycerine), and certain study medications (i.e., captopril) are contraindicated during pregnancy.

Table 5. Eligibility Criteria

Inclusion Criteria

- BMI ≥ 30 kg/m²
- Age ≥ 18 years
- HbA1c 5.7-6.4%
- Self reported sleep <7 hours per night

Exclusion Criteria

- Current or prior history of diabetes mellitus
- Use of hypoglycemic meds or random serum glucose ≥ 200 mg/dL
- Estimated GFR <60 mL/min/1.73m²
- Inability to extend sleep by 1 hour per night
- Pregnant or breast-feeding
- Preexisting lung disease requiring oxygen

- Preexisting CVD
- Active or uncontrolled psychotic disorder
- Active or uncontrolled bipolar illness
- Active malignancy within the prior 5 years
- Use of antihypertensive meds
- Hepatic impairment
- Job requires rotating night shifts
- Bariatric surgery within the prior 12 months
- Use of hypnotic meds
- Hematocrit <36%(women) or <41% (men)
- Use of natural sleep aids
- Known allergy/intolerance of ACE inhibitors
- History of stroke
- Recent (within 2 weeks of study) or upcoming travel across time zones

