- Known obstructive sleep apnea or use of continuous positive airway pressure
- Insomnia
- Known allergy to melatonin
- Hypertension Type 1 or 2 (BP >150/90)
- Lactose Intolerance
- Autoimmune Disease

[figure not shown]
Subject Enrollment

Responders to advertisements will be pre-screened by telephone to obtain a BMI estimate and a medical history to gauge potential eligibility (**Table 5**). For those who may be eligible following this phone query, the basic study schema (**Figure 1**) will be described to identify those who remain interested in participation after learning the duration, inpatient requirements, and potential medication use. These individuals will then be invited to attend an outpatient screening visit.

We anticipate that the sex and race/ethnicity breakdown of subjects enrolled into EMC-PILOT will be similar to that which we have experienced in the MODERATE trial. Thus far in the MODERATE trial, enrolled subjects are 63% female, 28% black, 7% more than one race, and 13% Hispanic.

The pilot study is a double-blind, placebo-controlled randomized trial, in which 16 subjects with obesity (BMI \geq 30 kg/m²), pre-diabetes (HbA1C, 5.7-6.4%), and self-reported short sleep duration (<7 hours/night) are randomly assigned 1:1 to receive either placebo or 2 mg of controlled-release melatonin, taken orally every evening 1 hour before bed for 6 weeks. **All subjects will be asked to extend their sleep time by one hour** during the 6 week period between inpatient visits. Endpoints will be measured at both the baseline and 6-week inpatient visits.

Figure 1: Schema for pilot study with sleep extension and nightly melatonin as treatments.

Screening Visit: Screening visits will take place at the Brigham and Women’s Outpatient Center for Clinical Investigation (CCI; [name]). During the outpatient screen, [name] will explain the study in detail, review the consent form, and answer questions. After obtaining written informed consent for participation, a history and physical examination will be performed in order initially judge eligibility based upon the criteria set out in **Table 5**. Those individuals deemed potentially eligible based upon the screening history and exam will undergo phlebotomy and analysis for HbA1c, serum chemistries and glucose, and CBC to confirm eligibility using the criteria presented in the table.

[figure not shown]
Study Procedures

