Pre-admission: All participants will wear a wrist activity monitor for a total of 8 weeks; 2 weeks prior to the baseline inpatient visit and for the 6 weeks between inpatient visits, **Figure 2**. They will complete a daily sleep log during the 2 weeks preceding the baseline visit and 6 weeks preceding second visit. Three days before admission, participants will be placed on a high salt diet by supplementing their usual diet with 150 mmol sodium/day for 3 days using dry bouillon added to food. All participants will also be asked to do a 24 hour diet recall for the day before admission.

Treatment assignments: Prior to admission for the baseline visit, **subjects will be randomized (1:1)** to receive study medication (melatonin 2mg of controlled release formulation or placebo). **All subjects will be asked to extend their sleep time by one hour** during the 6 week period between inpatient visits.

Baseline and Follow-up inpatient visit: Baseline and 6-week inpatient visits will be virtually identical. Each inpatient visit will begin at 4:00PM on Day 0 and end at 4:00PM on Day 1, **Figure 2**.

Figure 2: Schema for inpatient visit studies at 6-week visit.

Day 0 — We will complete two 12-hour urine collections for each subject. All subjects will begin the first 12-hour urine collection at their home at 7:00AM on day 0 of admission to the Brigham and Women’s Hospital Center for Clinical Investigation (CCI). The first 12-hour urine collection will be ended at 7:00PM that evening. The second 12-hour collection will begin and continued overnight until 7:00AM on day 1. The nurses will keep the daytime (7AM to 7PM) and nighttime (7PM to 7AM) urine separate to permit analysis of diurnal variation in urinary analytes. Subjects will fast after 9 pm to ensure a 12-hour fast by the next morning.

[figure not shown]

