Biostatistical analysis

The primary purpose of the trial is to generate pilot data for a larger randomized control trial.

Therefore we aim to calculate means and standard errors for the parameters as well as estimates of effects of sleep extension and melatonin supplementation which will allow accurate power calculations and facilitate the design of a larger study. While we suspect we will be underpowered in this study to find significant differences in endpoints due to sleep extension or melatonin supplementation we will perform statistical analysis on the outcomes as follows. For the main outcomes (renal specific RAAS, BP, glycemic control [insulin sensitivity and β -islet cell function]), we can assume a normal approximation for the changes in log transformed endpoints and so will use an ANCOVA analysis to compare the change in outcome from baseline to 6 week follow-up between melatonin (N=8) and placebo groups (N=8) of the study. Finally we will test the interaction of sleep extension and melatonin supplementation using multivariable linear regression of the parameter change with predictors which will include treatment assignments (sleep extension and melatonin supplementation) and the interaction term **sleep extension *melatonin supplementation** in an analysis of all study participants (N=16).

For the purposes of this grant we have performed power calculations for sleep extension based on either pilot data from obese individuals from our own studies or published results.

Renal specific RAAS Activity – Based upon published data, we assume that change in renal specific RAAS activity ($\Delta\text{RPF}_{\text{captopril}}$) is $46\text{ml}/\text{min}/1.73\text{m}^2$ in obese individuals, SD 12^{72} , and From these values, we estimate that we will have 80% power to detect a change in $\Delta\text{RPF}_{\text{captopril}}$ with sleep extension of $15\text{ml}/\text{min}/1.73\text{m}^2$ (33% from baseline) with type I error of 0.05 (two-tailed), **Table 7**.

Central Blood Pressure – Based on pilot data, we assume a mean central systolic BP of 106 mmHg and SD 10 mmHg with a between measurement correlation coefficient 0.89. Thus, for ANCOVA analysis the SD is 6.0 for change in BP. From these values, we estimate we will have 80% power to detect a change in BP of 8 mmHg due to sleep extension with type I error of 0.05 (two-tailed), **Table 7**.

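### Sleep extension is assigned to every participant, so the planned regression cannot estimate its effect or its interaction with melatonin

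*Combined protocol and SAP*

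**What the plan says.** Three places give sleep extension to the whole sample. Aim 1 under Specific Aims states that "20 individuals with habitual sleep restriction will all be asked to extend their nightly sleep by 1 hour". Subject Enrollment, and the treatment-assignment paragraph of Study Procedures, both state that "All subjects will be asked to extend their sleep time by one hour". Table 5 lists as an exclusion "Inability to extend sleep by 1 hour per night". The only randomised factor is study medication, melatonin or placebo, 1:1.

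The Biostatistical analysis section nevertheless treats sleep extension as something that varies between participants, in three ways:

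- It promises "estimates of effects of sleep extension and melatonin supplementation which will allow accurate power calculations and facilitate the design of a larger study".
- After an ANCOVA of melatonin (N=8) against placebo (N=8), it adds a regression of the change in each parameter on "predictors which will include treatment assignments (sleep extension and melatonin supplementation) and the interaction term" of the two, using all 16 participants.
- It attributes the detectable change for each of the five outcomes with a power statement to sleep extension.

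**The concern.** A regression can separate the effect of an assignment only if some participants have it and some do not. Here 8 melatonin plus 8 placebo already make up the full 16, and all of them extend sleep, so there is no unextended group. The sleep-extension term and the interaction have nothing to be estimated from.

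Two things are at stake. First, one of the two planned analyses returns either no result or a mislabelled one: if a routine keeps the product term and discards the melatonin term, the melatonin effect is printed as an interaction. Second, the pilot exists to supply inputs for a larger trial. Any sleep-extension effect it passed on would be a before-after change that may include regression to the mean, repeat-visit effects, placebo response and the effect of regular study contact.

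**Working it through.** **1. The plan's own figure: 80% power for a sleep-extension effect.** The inputs are the effects and SDs of change in the Biostatistical analysis section, taken as stated, with two-sided alpha 0.05. For a two-group t test with n per group, the noncentrality is effect / (SD × √(2/n)). For renal plasma flow response at 8 per group it is 15 / (12 × √(2/8)) = 2.50 on 14 df, which gives 64% power. For a one-group before-after t test it is effect / (SD / √n).

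| Outcome | Effect, SD | 8 vs 8 | 10 vs 10 | Before-after, n=16 |
|---|---|---|---|---|
| Renal plasma flow response | 15, 12 | 64% | 75% | >99% |
| Central systolic BP | 8, 6.0 | 70% | 81% | >99% |
| 24-hour systolic BP | 6, 5.0 | 61% | 72% | >99% |
| Insulin sensitivity | 1.4, 1.1 | 66% | 77% | >99% |
| Beta-cell response | 24, 17.68 | 71% | 82% | >99% |

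A before-after test in 8 people gives 83% to 91%. No single reading returns 80% throughout. The two-group t test reaches 80% at 10 to 12 per group, depending on the outcome, so the figures look like a between-group sleep-extension comparison. The trial has no such comparison.

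**2. The regression.** Let S be sleep-extension assignment (1 for everyone) and M melatonin assignment (1 or 0). The planned model is

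change = b0 + b1·S + b2·M + b3·S·M + error.

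Only two distinct rows of (intercept, S, M, S·M) occur:

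- placebo: (1, 1, 0, 0), expected change b0 + b1
- melatonin: (1, 1, 1, 1), expected change b0 + b1 + b2 + b3

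Two group means cannot determine four coefficients. The S column equals the intercept and the S·M column equals M. Built numerically, the matrix has rank 2 of 4 with 8 per arm and again with 10 per arm. Only the sums b0 + b1 and b2 + b3 are estimable; the second is the melatonin effect given sleep extension. Neither b1 nor b3 can be recovered.

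For contrast only, a 2×2 factorial with 4 per cell has rank 4, and its interaction has standard error √(4 × 1/4) = 1.0 residual SD. The documents describe no such design.

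**3. What can be estimated about sleep extension.** The cleanest quantity is the mean change in the placebo arm. Its 95% half-width, in units of the SD of change, is t / √n:

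- n=8, placebo-arm variance (7 df): 2.365 / √8 = 0.84
- n=8, variance pooled over both arms (14 df): 2.145 / √8 = 0.76
- n=10, placebo-arm variance (9 df): 2.262 / √10 = 0.72
- all 16 pooled (15 df): 2.131 / √16 = 0.53, but half of these participants also take melatonin

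With the plan's SDs, 0.84 SD is about 5.0 mmHg for central systolic BP (0.836 × 6.0) and 4.2 mmHg for 24-hour systolic BP (0.836 × 5.0). These intervals cover sampling error only, not the bias from having no control group.

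**The case against.** The strongest defence is that little depends on this regression. It comes last, after the randomised melatonin-versus-placebo ANCOVA, which is sound and unaffected, in a pilot that openly expects to be underpowered. That correctly limits the reach of the problem. It does not answer it: low power makes an estimate imprecise, whereas these two coefficients do not exist at any sample size, and a sleep-extension estimate is a named product of the pilot.

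Sleep extension could be read as achieved sleep, which the wrist monitor and sleep log record and which varies between people. But the model names treatment assignments, and a regression on achieved sleep would be a different, observational analysis. The power text could be read as referring to before-after change. Such a change can be computed, but the section specifies no before-after analysis, and the stated 80% does not match one.

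Some supporting points need to be kept in proportion. Regression to the mean is possible but not shown: entry is on BMI, HbA1c, self-reported sleep and a BP ceiling, not on renal plasma flow response or modelled insulin sensitivity. The two-weekly calls about the sleep schedule are plausibly part of delivering sleep extension rather than a separate influence. How a program handles duplicated columns depends on the routine, and the plan names none for the regression. The half-width is 0.72 to 0.84 SD for the placebo arm, depending on the variance used and on whether 16 or 20 are enrolled. None of this changes the rank.

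**Conclusion.** The concern holds. Two of the four terms in the planned regression, the sleep-extension effect and the interaction, cannot be estimated, and the promised effect of sleep extension cannot be obtained as a controlled estimate. The conclusion rests only on the repeated statement that everyone is asked to extend sleep. It does not depend on the SDs, on the power figures, or on the unresolved discrepancy between 16 and 20 participants. The randomised estimate of melatonin on a background of sleep extension stands. This must be corrected before the analysis is run, because it affects a stated deliverable of the pilot.

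**What to change.** In the Biostatistical analysis section:

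- Delete the sleep-extension term and the interaction term.
- Keep one randomised contrast, melatonin versus placebo on a background of sleep extension, by ANCOVA with the baseline value named as covariate.
- Report the baseline-to-6-week change in the placebo arm with a 95% confidence interval, labelled as uncontrolled.
- Withdraw the statements that the pilot estimates a sleep-extension effect or an interaction.
- If a sleep-dose analysis is wanted, use the change in sleep duration from the wrist monitor, already worn for 8 weeks, as an exploratory, non-randomised predictor.

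For consistency, re-base the power paragraphs and Table 7 on the melatonin contrast or on the labelled before-after change, reword Aim 1 so that it does not imply a controlled test of sleep extension, and state one sample size throughout.

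The cost is text changes only; enrolment, procedures and data collection stay as they are. A controlled sleep-extension effect or an interaction would need a randomised comparison group without sleep extension, which is a different design and a matter for the larger trial.

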24 hour Ambulatory Blood Pressure – Based on pilot data, we assume a mean 24-hour systolic BP of 122.8 mmHg and SD of 10.4mmHg with a between-measurement correlation coefficient 0.74. Thus for ANCOVA analysis the SD is 5.0 for change in BP. From these values, we estimate that we will have 80% power to detect a 6 mmHg change in 24-hour mean SBP due to sleep extension with a type I error rate of 0.05 (two-tailed).

Insulin sensitivity –Based on published data, we assume a mean insulin sensitivity of 19.03 dl/kg/min/pmol/l and SD of 1.38 dl/kg/min/pmol/l and a between-measurement correlation coefficient of 0.7.^{2,73} Thus for ANCOVA analysis the SD for change in insulin sensitivity is 1.1 dl/kg/min/pmol/l. From these values we estimate that we will have 80% power to detect a change in insulin sensitivity of 1.4 dl/kg/min/pmol/l due to sleep extension with type I error of 0.05 (two-tailed), **Table 7**

β -islet cell responsitivity – Based on published data, we assume a mean β islet cell response (dynamic response, ϕ_d) of 494.88 and SD of 25.16 and a assume a measurement correlation coefficient of 0.7.^{2,73} . Thus for ANCOVA analysis the SD for change in ϕ_d is 17.68. From these values we estimate that we will have 80% power to detect a change in β islet cell response of 24 due to sleep extension with type I error of 0.05 (two-tailed), **Table 7**. All power calculation performed with PS power and sample size calculator, version 3.0.34.

Table 7: Comparison of the change in outcome we are powered to detect compared with measured changes in outcomes detected in other studies with lifestyle interventions or BMI comparisons.

Outcome	Intervention/Comparison	Δ Measured	Detectable change in this study
Renal Specific RAAS ⁷²	Obese vs overweight	9ml/min/1.73m ²	15ml/min/1.73m ²
Central systolic BP ⁴⁶	Diet and exercise	12 mmHg	8mmHg
24hour ABPM ⁴⁷	Difference in BMI of 5kg/m ²	3 mmHg	6mmHg
Insulin Sensitivity ²²	Diet and exercise	19% change	7% change
β -islet cell function ⁴⁰	Diet	20% change	5% change

Risks and Discomforts

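### The five 80% power claims are for sleep extension, which has no comparison group, and give no n; applied to melatonin versus placebo with the printed SDs, power is 61–71% at 8 per arm and 72–82% at 10

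*Combined protocol and SAP*

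**What the plan says.** The Biostatistical analysis section introduces its calculations with "For the purposes of this grant we have performed power calculations for sleep extension based on either pilot data". It then claims 80% power at a two-sided 0.05 level for a change in renal-specific RAAS activity, central systolic BP, 24-hour systolic BP, insulin sensitivity and beta-cell response. Each claim is worded as an effect of sleep extension; for central BP it reads "we estimate we will have 80% power to detect a change in BP of 8 mmHg due to sleep extension". The last column of Table 7 repeats the five changes as what this study can detect. None of the statements gives an n or names the test.

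The same section opens with a caveat: "While we suspect we will be underpowered in this study to find significant differences in endpoints due to sleep extension or melatonin supplementation". It defines the planned test as an ANCOVA "to compare the change in outcome from baseline to 6 week follow-up between melatonin (N=8) and placebo groups (N=8) of the study".

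On design, Specific Aims states that "20 individuals with habitual sleep restriction will all be asked to extend their nightly sleep by 1 hour" before 1:1 randomisation to melatonin or placebo. Study Procedures repeats: "All subjects will be asked to extend their sleep time by one hour".

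The sample size is 16 in Subject Enrollment and in Biostatistical analysis (8 and 8), but 20 in Specific Aims and in Potential Benefits (10 and 10 in the latter).

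**The concern.** A power figure describes a particular contrast, sample size and SD. Here the named contrast does not exist between groups, because nobody is assigned to keep their usual sleep. The contrast that is randomised and analysed has no power statement. With no n given and two sample sizes in the document, the basis of the 80% cannot be recovered.

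The pilot exists to inform the design of a larger trial. Someone who uses Table 7 to judge this study, or as a starting point for the next one, would read its last column as what the randomised comparison can detect. With the printed SDs, 8 against 8 cannot detect those changes with 80% power. The 80% claims also sit a few lines below a sentence that says the opposite.

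**Working it through.** **Inputs**, all from Biostatistical analysis: two-sided alpha 0.05, the stated change Δ, and the SD printed for each endpoint. For renal RAAS the only SD given is 12, for the captopril response itself. No correlation is given, so 12 is treated here as the SD of change, which is an assumption.

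**Step 1. Can the 80% be reproduced?** The standardised changes d = Δ/SD are 15/12 = 1.25, 8/6.0 = 1.33, 6/5.0 = 1.20, 1.4/1.1 = 1.27 and 24/17.68 = 1.36. Because they differ, no single n gives 80% within two points for all five. The closest match is a normal approximation with 10 per group: detectable change = (1.960 + 0.842) × SD × √(2/10) = 1.253 × SD, or 15.0, 7.5, 6.3, 1.38 and 22.2. Four of these round to the stated 15, 8, 6 and 1.4; the fifth is stated as 24. The document does not say that this was the calculation, and its analysis paragraph gives 8 per group.

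**Step 2. Melatonin versus placebo, printed SDs.** Two-sample t-test with non-centrality d × √(n/2) and 2n − 2 degrees of freedom. The change detectable with 80% power is 1.507 × SD at 8 per arm and 1.325 × SD at 10 per arm.

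| Endpoint | Stated Δ | Power, 8/arm | Power, 10/arm | Detectable, 8/arm | Detectable, 10/arm | n/arm for 80% |
|---|---|---|---|---|---|---|
| Renal RAAS | 15 | 64% | 75% | 18.1 | 15.9 | 12 |
| Central SBP | 8 | 70% | 80.5% | 9.0 | 7.95 | 10 |
| 24-h SBP | 6 | 61% | 72% | 7.5 | 6.6 | 12 |
| Insulin sensitivity | 1.4 | 66% | 77% | 1.66 | 1.46 | 11 |
| Beta-cell response | 24 | 71% | 82% | 26.6 | 23.4 | 10 |

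Taking one degree of freedom for the ANCOVA covariate lowers power by about half a point. The normal approximation gives 67–77% at 8 per arm, still below 80% for all five, and 77–86% at 10.

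**Step 3. SDs implied by the stated SD and correlation.** ANCOVA SD = SD × √(1 − r²):

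- Central SBP: 10 × √(1 − 0.89²) = 4.56 (printed 6.0)
- 24-h SBP: 10.4 × √(1 − 0.74²) = 7.00 (printed 5.0)
- Insulin sensitivity: 1.38 × √(1 − 0.7²) = 0.986 (printed 1.1)
- Beta-cell response: 25.16 × √(1 − 0.7²) = 17.97 (printed 17.68)

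The 24-hour SBP mismatch is the largest. The text has "SD of 10.4mmHg with a between-measurement correlation coefficient 0.74" followed by "Thus for ANCOVA analysis the SD is 5.0 for change in BP". With the implied SDs, in the order listed:

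- Power is 90, 36, 75 and 70% at 8 per arm, and 96, 44, 85 and 81% at 10.
- Detectable changes are 6.9, 10.5, 1.48 and 27.1 at 8 per arm, and 6.0, 9.3, 1.31 and 23.8 at 10.

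**Step 4. Reading the claims as an uncontrolled pre-post change.** One-sample t-test with non-centrality d × √n. With the printed SDs, power is 83–91% at n = 8 (for example the placebo arm alone, which keeps melatonin out) and above 99% at n = 16 or 20. So 80% does not describe the full sample on this reading; it corresponds to about 7 or 8 people. For 24-hour SBP the implied change SD is 10.4 × √(2 × (1 − 0.74)) = 7.50, which gives 50% at n = 8, 85% at n = 16 and 92% at n = 20.

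**The case against.** The strongest reply is that the plan never promises 80% power for melatonin versus placebo, so the 61–71% contradicts no printed figure. That is right as far as it goes: the direct fault is that power is claimed for a contrast with no concurrent control and no n. The melatonin figures show what the stated changes amount to in the one comparison the plan will run.

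A second reply is that the study is an openly declared pilot, expected to be underpowered, with calculations included for a grant and no success criterion tied to them. This lowers the stakes, but it leaves the caveat and the 80% claims in contradiction.

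Third, most of the gap depends on n. At 10 per arm the detectable changes lie within about 10% of those stated, and the normal approximation at 10 per group nearly recovers them. That stands, and it is a reason to settle 16 or 20 first. It does not rescue 8 per arm.

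Two technical limits also stand. The renal RAAS figures rest on reading SD 12 as a change SD; the sentence giving it is incomplete, possibly from PDF extraction. And the plan analyses log-transformed changes, while its power inputs, and so these recalculations, are on the raw scale.

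**Conclusion.** The concern holds. The five 80% statements belong to a contrast the design does not contain and carry no n. Transferred to melatonin versus placebo with the printed SDs, none reaches 80% at 8 per arm. At 10 per arm only central SBP and beta-cell response do, with insulin sensitivity close at 77%.

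Replacing the printed SDs by those implied by the stated SD and correlation moves the results both ways: central SBP does better than stated and 24-hour SBP much worse. A pre-post reading does not repair the claims, because it cannot attribute the change to sleep extension and is not the planned ANCOVA.

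These figures assume a two-sided t-test at 0.05, raw-scale SDs and no dropout; any loss would lower them. This should be fixed, but it does not undermine the trial's purpose as a pilot.

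**What to change.** 1. Reconcile 16 and 20 participants across Specific Aims, Subject Enrollment, Biostatistical analysis and Potential Benefits.
2. State power for melatonin versus placebo, with the n per arm and the test used. If a sleep-extension figure is kept, label it as an uncontrolled pre-post change and give its n (placebo arm or all participants) and its SD.
3. Reconcile each change SD with the stated SD and correlation, supply the missing renal RAAS input, and recompute the last column of Table 7 at the agreed n. The values above show the range and are not final entries.
4. Bring the 80% wording into line with the sentence that expects the study to be underpowered.

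The cost is rewording in one section, one table column and one consistent sample size. It needs no added participants, visits or delay. With the SDs implied by the plan's own inputs, the 24-hour SBP entry would become less favourable and central SBP more so.
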